1. STUDY DETAILS

This is the statistical analysis plan (SAP) for study D5180C00007. The SAP describes the statistical analyses specified in the latest version of the clinical study protocol (CSP) in more detail; any changes to what is specified in the CSP will be described in [Section 6](#).

1.1 Study objectives

1.1.1 Primary objective

Objective:	Endpoint/variable:
To assess the effect of 210 mg tezepelumab SC Q4W on asthma exacerbations in adult and adolescent subjects with severe uncontrolled asthma compared with placebo	Primary endpoint: Annualised asthma exacerbation rate (AAER) Primary outcome measure: AAER ratio versus placebo over 52 weeks

1.1.2 Key secondary objectives

Objective:	Endpoint/variable:
To assess the effect of 210 mg tezepelumab SC Q4W on pulmonary function compared with placebo	Key secondary: Change from baseline in pre-dose/pre-bronchodilator (pre-BD) forced expiratory volume in 1 second (FEV ₁) Key outcome measure: Mean difference vs placebo at Week 52
To assess the effect of 210 mg tezepelumab SC Q4W on health status/health related quality of life compared with placebo	Key secondary: Change from baseline in Standardized Asthma Quality of Life Questionnaire for 12 years and older (AQLQ(S)+12) total score Key outcome measure: Mean difference vs placebo at Week 52

Objective:	Endpoint/variable:
To assess the effect of 210 mg tezepelumab SC Q4W on asthma control compared with placebo	
Key secondary: Change from baseline in Asthma Control Questionnaire-6 (ACQ-6) score
 
Key outcome measure: Mean difference vs placebo at Week 52

To assess the effect of 210 mg tezepelumab SC Q4W on asthma symptoms compared with placebo	
Key secondary: Change from baseline in weekly mean daily Asthma Symptom Diary score
 
Key outcome measure: Mean difference vs placebo at Week 52

1.1.3 Other secondary objectives

Objective:	Endpoint/variable:
To assess the effect of 210 mg tezepelumab SC Q4W on other endpoints associated with asthma exacerbations	
Outcome variable: Time to first asthma exacerbation
 
Outcome measure: Asthma exacerbation hazard ratio vs placebo over 52 weeks
 
Outcome variable: Proportion of subjects who did not experience an asthma exacerbation over 52 weeks
 
Outcome measure: Difference in proportions vs placebo at Week 52
 
Outcome variable: Annualised rate of exacerbations associated with emergency room visit or hospitalisation
 
Outcome measure: AAER ratio vs placebo over 52 weeks

Objective:	Endpoint/variable:
To assess the effect of 210 mg tezepelumab SC Q4W on biomarkers	
Outcome variables: Change from baseline in
 
• Clinic based fractional exhaled nitric oxide FENO (ppb)• peripheral blood eosinophils• total serum IgE 
Outcome measure: Mean difference vs placebo at Week 52

To assess the effect of 210 mg of tezepelumab SC Q4W on other asthma control metrics	
Outcome variables: Change from baseline in
 
• weekly mean rescue medication use• weekly mean morning and evening home-based peak expiratory flow (PEF)• weekly mean number of night-time awakenings 
Outcome measure: Mean difference vs placebo at Week 52
 
Further details clarifying the definitions of these endpoints are given in Section 3.2.4.3 and Section 3.2.4.4.

Objective:	Endpoint/variable:
To assess the effect of 210 mg tezepelumab SC Q4W compared with placebo on health resource utilization and productivity loss due to asthma	
Outcome variables:
 
 • Asthma specific resource utilization (e.g. unscheduled physician visits, unscheduled phone calls to physicians, use of other asthma medications) • Work Productivity and Activity Impairment (WPAI+CIQ) Questionnaire and Classroom Impairment Questionnaire score 
Outcome measures:
 
 • Difference in number of asthma specific resource utilizations vs placebo over 52 weeks • Difference in WPAI+CIQ score vs placebo at Week 52
To evaluate the pharmacokinetics (PK) and immunogenicity of tezepelumab	
PK: Serum concentrations Immunogenicity: Incidence of anti-drug antibodies

To assess the effect of 210 mg tezepelumab SC Q4W on general health-related quality of life	
Outcome variable: European Quality of Life – 5 Dimensions 5 Levels Questionnaire (EQ-5D-5L) score Outcome measure: Mean difference vs placebo at Week 52

To assess the effect of 210 mg of tezepelumab SC Q4W on patient (PGI-C and PGI-S) and clinician impression of overall asthma severity (CGI-C)	
Outcome variable: Patient Global Impression of Change/Severity (PGI-C, PGI-S) and Clinician Global Impression of Change (CGI-C) Outcome measures: Proportions of responses at Week 52

1.1.4 Safety objectives

Objective:	Endpoint/variable:
To evaluate the safety and tolerability of tezepelumab	Adverse events/serious adverse events Vital signs Clinical chemistry/haematology/urinalysis parameters Digital electrocardiograms

1.1.5 Exploratory objectives

CCI	
[Redacted]	[Redacted]
[Redacted]	[Redacted]
[Redacted]	[Redacted]
[Redacted]	[Redacted]
[Redacted]	[Redacted]
[Redacted]	[Redacted]
[Redacted]	[Redacted]
[Redacted]	[Redacted]

CCI

[REDACTED]	[REDACTED]
[REDACTED]	[REDACTED]
[REDACTED]	[REDACTED]
[REDACTED]	[REDACTED]
[REDACTED]	[REDACTED]

1.2 Study design

This is a phase 3, multicentre, randomised, double-blind, placebo-controlled, parallel group study to evaluate the effect of 210 mg of tezepelumab administered Q4W SC in adult and adolescent subjects with severe uncontrolled asthma, who have a history of 2 or more exacerbations in the previous 12 months.

All subjects must have been receiving medium or high dose inhaled corticosteroids (ICS) for at least 3 months prior to screening. Further, all subjects must have been on at least one additional asthma controller medication according to standard practice of care, with or without oral corticosteroids (OCS), in the 3 months prior to screening.

The study will randomise approximately 1060 subjects globally in a 1:1 ratio to either:

- Tezepelumab 210mg every 4 weeks (Q4W) by subcutaneous (SC) injection, or
- Placebo Q4W by SC injection.

Approximately 80 adolescents are expected to be included. Randomisation will be stratified by:

- Region [Western Europe plus Australia; South America; North America; Asia Pacific; Central/Eastern Europe; Rest of World], and
- Age group at screening [adult (18-80 years); adolescent (12-17 years)].

The randomised study population will be monitored throughout recruitment to ensure a broad subject distribution across key clinical factors, and limits may be placed on subsequent randomisation within certain subgroups if necessary. This monitoring will be performed overall and by region. It may be applied to the adult population instead of the overall population to avoid difficulties with adolescent recruitment, if this becomes necessary. The clinical factors which will be monitored, and the target percentages anticipated to be used for this monitoring, are:

- Exacerbation history in previous 12 months (at least 40% subjects with ≥ 3 exacerbations; at most 60% subjects with exactly 2 exacerbations)
- Background ICS dose level (at most 20% subjects on medium ICS dose; at least 80% subjects on high ICS dose)
- Eosinophil level at screening (50% subjects with < 300 eosinophils/ μL ; 50% subjects with ≥ 300 eosinophils/ μL). The proportions of subjects with < 150 eosinophils/ μL and ≥ 150 eosinophils/ μL , and with < 450 eosinophils/ μL and ≥ 450 eosinophils/ μL , will also be monitored.

The study will consist of a screening/run in period between 5-6 weeks, a planned treatment period of 52 weeks and a post-treatment follow-up period of 12 weeks. The follow-up period may not apply to subjects who participate in the extension study. Any data collected after a subject is enrolled in the extension study will not be included in the analyses described in this SAP.

During the planned treatment period, investigational product (IP) will be administered Q4W starting at the randomisation visit (Week 0; Day 1), with the last administration occurring at Week 48. IP will not be administered at Week 52. Subjects who prematurely discontinue IP will be encouraged to remain in the study and undergo appropriate study visits/procedures for the full planned 52-week treatment period, despite no longer receiving treatment. At the IP Discontinuation (IPD) visit, the subject will be given the following 3 options (further details are given in the CSP Section 7.1.1):

1. The subject should be encouraged to return for all regular clinic visits and perform all scheduled assessments until he/she completes a total of 52 weeks in the study (the planned treatment period)
2. The subject will be offered follow-up on a monthly basis via telephone calls while continuing eDiary and PEF completion (no further procedures will be performed), until the subject completes 52 weeks in the study
3. If the subject cannot or does not wish to comply with either of the options above (or any component of them, such as only telephone-based visits without completion of the eDiary and PEF), then the investigator will only contact the subject at 52 weeks post-randomisation. No study assessments will be performed prior to this contact.

1.3 Number of subjects

Approximately 1060 subjects will be randomly assigned to study treatment using 1:1 allocation between the two treatments. Since the primary analysis of the primary endpoint will include all available data, including after treatment discontinuation, no need is envisaged to adjust the number of subjects planned to be randomised in order to obtain a number of evaluable subjects.

With 530 subjects per treatment group it is estimated that, using the multiple testing procedure described in [Section 4.1.2](#) with an overall Type 1 error control at $\alpha=0.05$ and a Type 1 error control for the primary endpoint at $\alpha=0.01$, the power for the primary and the key secondary endpoints will be at least 90%. The Type 1 error control at $\alpha=0.01$ for the primary endpoint is chosen to further ensure statistically persuasive evidence.

For the primary endpoint, assuming a placebo rate of 0.9 per year, a shape parameter of 2.4 (overdispersion), and a dropout rate of 10% (assumed uniform over the study), there will be at least 99% power to detect a rate reduction of 50% at a 2-sided significance level of 1%. The methodology used is as described in [Keene et al., 2007](#), and developed further by [Zhu and Lakkis, 2014](#). The minimum rate reduction that would yield statistical significance with the above assumptions is 27%.

For AAER in subjects with baseline eosinophils $< 300/\mu\text{L}$, assuming a placebo rate of 0.6 and assuming that half of subjects will be in this subgroup (i.e. 265 subjects per treatment group), there will be 94% power to detect a rate reduction of 50% at a 2-sided significance level of 5%, with the same shape parameter and dropout assumptions as above.

For each of the following four key secondary endpoints, change from baseline in pre-BD FEV₁, change from baseline in AQLQ(S)+12 total score, change from baseline in ACQ-6, and change from baseline in weekly mean Asthma Symptom Diary score, the nominal power is 95% or higher (using a nominal 2-sided significance level of 5%), assuming standard deviations of 400 mL and 1.3, 1.3, and 1.3 units respectively, and true differences of 100 mL and 0.3, 0.3, and 0.3 units respectively. The minimum detectable differences, under the above assumptions, are 50 mL for FEV₁, 0.16 for AQLQ(S)+12 total score, and -0.16 for each of Asthma Symptom Diary score and ACQ-6 score.

The above effect size and variability assumptions are taken from the Phase IIb tezepelumab trial as reported in [Corren et al., 2017](#).

2. ANALYSIS SETS

2.1 Definition of analysis sets

All subjects analysis set

This analysis set comprises all enrolled subjects who signed the informed consent form, including screening failures, and will be used for the reporting of disposition.

Randomised subjects analysis set

This analysis set comprises all subjects randomised to study treatment, irrespective of whether IP was subsequently taken, and will also be used for the reporting of disposition.

2.1.1 Efficacy analysis set

Full analysis set (FAS)

This analysis set comprises all subjects randomised to study treatment who received at least one dose of IP, irrespective of their protocol adherence and continued participation in the study.

Efficacy analyses will be performed using all subjects in the FAS, according to the intent-to-treat (ITT) principle. Subjects will be analysed according to their randomised treatment (including in the case of any discrepancies between randomised and actual treatment).

The FAS specifies which subjects are included in efficacy analyses. Details of which data are included in efficacy analyses for these subjects are given in the respective sections, notably in [Section 2.1.5](#), [Section 3.1.4](#) and [Section 4.2](#).

For consistency with efficacy analyses, demographics and baseline characteristics will be summarised using the FAS.

Certain types of exploratory efficacy data are planned to be captured in a subset of participating subjects who have given an additional consent to participate in such a sub-study. Where this is the case, the analysis will use the subset of subjects in the FAS for which any data of the relevant type are available. No formal sub-study analysis sets will be explicitly defined for this purpose.

2.1.2 Safety analysis set

Safety analysis set

This analysis set comprises all subjects who received at least one dose of IP.

Safety analyses will be performed using all subjects in the safety analysis set. Subjects will be analysed according to their actual treatment in the case of any discrepancies between randomised and actual treatment. Specifically, a subject who has on one or more occasion actually received active (tezepelumab) treatment will be assigned to the tezepelumab group, regardless of the randomised treatment assignment. A subject who has on no occasion actually received any active (tezepelumab) treatment will be assigned to the placebo group, regardless of the randomised treatment assignment.

Safety data will also be listed separately and discussed in the CSR for any subject who received a treatment at one or more visits which was not the randomised treatment.

Summaries of anti-drug antibodies (ADA) will also be based on the safety analysis set, using the same approach to handle treatment dispensing errors.

2.1.3 Other analysis set

PK analysis set

This analysis set comprises all subjects in the FAS who received active (tezepelumab) treatment and had at least one detectable serum concentration from a PK blood sample collected post first dose which is assumed not to be affected by factors such as protocol deviations.

2.1.4 Handling of other issues which may impact analysis sets

If it is found that any subject has been randomised on more than one occasion (contrary to the protocol) under different subject numbers, either at the same site or at different sites, then data corresponding to the first subject participation will be used in the analyses. Data associated with the second (and any subsequent) participation of the same subject will be listed and discussed in the CSR. All data associated with duplicate randomisations will be reviewed, and decisions regarding the analysis and reporting of these data will be documented, prior to unblinding at the primary database lock.

The above analysis set definitions assume the integrity of data captured from all participating sites in the trial. If it is deemed necessary to exclude subjects from analysis sets due to suspected fraud/other serious non-compliance at a particular site, or to perform sensitivity analyses with subjects from such a site removed for the same reason, this will be documented in this SAP (amended if necessary) where this is possible prior to primary database lock. Otherwise, it will be fully described in the CSR. The SAP will not be updated for this after primary database lock.

2.1.5 Definition of on-treatment

Efficacy analyses

Any efficacy assessment date which occurs between the date of randomisation and minimum (date of last dose of IP + 33 days, date of death, date of study withdrawal) will be considered on-treatment. In particular, this allows a subject who completes treatment according to the protocol to have their Week 52 data included as on-treatment, provided Week 52 is within the protocol visit window after the last dose of IP at Week 48.

Safety analyses

Safety analyses will be presented for subjects in the safety analysis set, which is described further in [Section 2.1.2](#).

For this purpose, any adverse event start date, or any safety assessment date (e.g. laboratory, vital signs), which occurs between the date of first dose of IP and minimum (date of last dose of IP + 33 days, date of death, date of study withdrawal) will be considered on-treatment. In particular, this allows inclusion of any safety-related information which may be reported at or generated from the IPD visit to be considered as on-treatment, provided the IPD visit is within the protocol visit window after premature discontinuation of IP.

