- ^w Subjects completing the EOT period, may be eligible to enroll in a separate extension study D5180C00018 and that these subjects will not complete the follow-up visits at Week 58 and Week 64. During the Corona Virus Disease 2019 (COVID-19) pandemic, subjects enrolling in the separate extension study D5180C00018 will continue participation in the follow-up visit(s) (Week 58, Week 64) until the on-site visit (or alternate site) for extension study randomization and IP administration can be conducted.

EOT End-of-Treatment; FU Follow-up; IPD Investigational Product Discontinuation; UNS Unscheduled; W Week.

CHANGES REQUIRED DURING THE COVID-19 PANDEMIC

Please Note: Changes below should only be implemented during the COVID-19 pandemic.

During the COVID-19 pandemic, changes are being implemented in order to ensure the safety of study subjects, to maintain compliance with good clinical practices, and to minimize risks to data integrity. Where allowable by local health authorities, ethics committees and healthcare provider guidelines (e.g. hospital policies), these changes include:

- The option of home visits including home administration of Investigational Product (IP) performed by a qualified Health Care Professional (HCP). Additional information related to the visit can be obtained remotely by phone call and/or video conference. The rationale for this change is to minimize the risk of subjects missing scheduled IP administration and visit assessments due to inability/unwillingness to visit the site during the COVID-19 pandemic.
- Remote visits (phone call and/or video conference) to replace on-site visits, if subjects cannot attend the visits at the study site,

at an alternate site or have home visits. The rationale for this change is to ensure that assessments and collection of information continue for visits that cannot be done at the site, at an alternate site or at the subject's home. This will reduce the risk of subject exposure to COVID-19

- Subjects aimed to transition to the extension study D5180C00018 to continue participation in the safety follow-up visit(s) (Week 58, Week 64) until the on-site (or alternate site) extension study randomization and IP administration can be conducted. The rationale for this change is to ensure randomization/first IP administration in the extension study D5180C00018 can be performed at the site (or alternate site) and to increase the chances of subjects transitioning to the extension study.

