The study will consist of a screening/run in period between 5-6 weeks, a treatment period of 52 weeks and a post-treatment follow-up period of 12 weeks. During the treatment period, IP will be administered starting at Day 0 until week 48. IP will not be administered on week 52. Subjects who discontinue IP during the study will be encouraged to undergo appropriate study visits/procedures for the full 52-week period. Further information is provided in section 7.1.1. Any new treatments that are initiated will be recorded in the eCRF.

Subjects who complete the 52-week study visit will complete a 12-week post treatment - follow-up period for the assessment of safety and anti-drug antibodies. Subjects that complete the planned treatment period as defined in the protocol (see Section 1.2) may be eligible to enroll in a separate extension study (these patients will not attend the Follow-up visits at Week 58 and Week 64). All other patients will attend the follow up visits.

During the screening/run-in period the subject must undergo all assessments per Table 1.

Prior to randomization the subjects must meet all inclusion /exclusion criteria. If a subject does not meet all inclusion criteria or meets any exclusion criteria as per section 5.1 and section 5.2, the subject will be screen failed. Rescreening is allowed only once. Further details are specified in section 5.4.

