3.1.4 Study periods

The following study periods are defined for analysis purposes:

- Screening/run-in period: starting on the date of the first study procedure and ending one day prior to randomisation (for randomised subjects) or on the date of the last study procedure (for screening failures). If any subject is re-screened, the latest available screening will be used for this purpose.
- Planned treatment period (on-treatment and off-treatment): starting on the date of randomisation (efficacy) / date of first dose of IP (safety) and ending on the date of the Week 52 visit or earlier study withdrawal date (for subjects not followed up until Week 52).
- On-treatment period: starting and ending on the start and end dates defined in [Section 2.1.5](#) for efficacy and safety analyses, respectively.
- Post-treatment period/Follow-up period: starting one day after the end date of the on-treatment period defined in [Section 2.1.5](#) for efficacy and safety analyses, respectively, and ending on the study completion or withdrawal date. Note: for subjects entering the extension study, the study completion date will be the day of enrolment in the extension study.
- On-study period (planned treatment and follow-up): starting on the date of randomisation (efficacy) / date of first dose of IP (safety) and ending on the study completion or withdrawal date. Note: for subjects entering the extension study, the study completion date will be the day of enrolment in the extension study. For analysis performed at primary database lock, the on-study period is understood to include all data recorded up until the date of the data cut-off for the primary

database lock (which includes all follow-up data available at the time of the data cut-off).

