3.1.8 Disposition

The following definitions will be used for time to event variables in Kaplan-Meier disposition plots:

Time to last dose of IP

Time to last dose of IP will be defined as follows:

$$\text{Time to last dose (days)} = [\text{Date of last dose of IP from eCRF} - \text{date of first dose of IP}] + 1.$$

Date of last dose of IP will be the date of last dose taken from the “Discontinuation of Investigational Product” eCRF page for all subjects; those who prematurely discontinue IP as well as those who complete IP dosing as per protocol.

Time to premature study withdrawal

Time to premature study withdrawal will be defined as follows:

Time to premature study withdrawal (days) = [study withdrawal date from eCRF – date of randomisation] + 1.

Study withdrawal date will be the completion or discontinuation date from the “Disposition” eCRF page, where any subject status other than “Completed” has been entered.

Subjects who did not prematurely withdraw from study will be censored at one of the following dates:

- Completion or discontinuation date from the “Disposition” eCRF page, where subject status of “Completed” has been entered.
- At primary DBL, ongoing subjects will be censored at their last contact date.

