3.3 Derivation of safety variables

3.3.1 Exposure to IP and treatment compliance

Extent of exposure to IP is defined as the number of days between the date of first dose of IP and the date of last dose of IP inclusive plus the number of days allowance for the dosing interval specified in [Section 2.1.5](#), that is:

$$\text{Extent of exposure (days)} = \text{minimum (date of last dose of IP + 33 days; date of death; date of study withdrawal)} - \text{date of first dose of IP} + 1$$

This calculation does not consider any gaps in exposure caused by the subject missing one or more intermediate scheduled 4-weekly doses. Such cases will be identified in the CSR if they occur, but will not explicitly be accounted for in any analysis.

The total subject-years exposure for a treatment group will be derived as the sum of the individual subject extents of exposure (days) for that treatment group and divided by 365.25.

Treatment compliance will be calculated as follows:

$$\text{Treatment compliance (\%)} = \left[\frac{\text{Total number of actual dosing occasions}}{\text{total number of expected dosing occasions}} \right] \times 100\%$$

In order to allow for subjects who discontinue IP early in the compliance calculation, the number of expected dosing occasions will be calculated as the number of scheduled dosing visits up to and including the last available dosing visit for that subject.

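### On-treatment time and extent of exposure are not capped at study completion, so subjects entering the extension at Week 52 accrue exposure days in which no event can be counted

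*SAP*

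**What the plan says.** SAP 2.1.5 closes the on-treatment period, for efficacy and for safety, at "minimum (date of last dose of IP + 33 days, date of death, date of study withdrawal"). SAP 3.3.1 closes extent of exposure at "minimum (date of last dose of IP + 33 days; date of death; date of study withdrawal"). The same minimum classifies concomitant medication in 3.1.6 and adverse events in 3.3.2.

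Withdrawal and completion are separate dates in the SAP. Section 3.1.8 takes the withdrawal date from the disposition page only "where any subject status other than “Completed” has been entered". Section 3.1.4 ends the post-treatment and on-study periods at completion or withdrawal, and notes that "for subjects entering the extension study, the study completion date will be the day of enrolment in the extension study". Section 1.2 adds: "Any data collected after a subject is enrolled in the extension study will not be included in the analyses described in this SAP".

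IP is given every 4 weeks "with the last administration occurring at Week 48" (SAP 1.2). The Protocol (Synopsis and overall design) says of extension entrants that "these patients will not attend the Follow-up visits at Week 58 and Week 64". There is a COVID-19 exception in the Schedule of Activities: "subjects enrolling in the separate extension study D5180C00018 will continue participation in the follow-up visit(s) (Week 58, Week 64) until the on-site visit" for the extension can be held.

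**The concern.** A subject who finishes treatment and moves into the extension has a completion date but no withdrawal date. Nothing in the minimum stops the clock when that subject leaves the study, so exposure continues to 33 days after the last dose even though anything observed after enrolment is discarded.

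Two things follow. First, the denominator contains time that cannot contribute to the numerator. That denominator feeds the exposure summaries (SAP 4.2.3) and the exposure-adjusted rates for all AEs and each AESI, reported per 100 subject-years (SAP 4.2.8.1). Section 2.1.5 is also the stated time at risk for on-treatment exacerbation analyses (SAP 3.2.1.1). The error always lowers the rate. Second, the period definitions contradict each other for these subjects, so a programmer must make an undocumented choice.

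The surplus days may also fall under extension dosing, since the COVID-19 text links the extension visit to randomisation and IP administration in that study. The documents give no extension dosing dates, so this is only a possibility.

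**Working it through.** **Inputs.** Target days: Week 48 = Day 337, Week 52 = Day 365 (SAP 3.1.5, Table 1). Allowance after last dose: 33 days (SAP 2.1.5). Visit windows at Weeks 48 and 52: ±5 days (Protocol, Table 2). Subjects per arm: 530 (SAP 1.3). Assumptions: first dose on Day 1; enrolment in the extension at the Week 52 visit; roll-over share r between 25% and 100%, because the documents do not give it.

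**Reproducing the 33 days.** Dosing interval plus visit window: (365 − 337) + 5 = 33. This agrees with the purpose stated in SAP 2.1.5, which is to keep an in-window Week 52 visit on-treatment.

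**One entrant, nominal timing.**
- On-treatment end: 337 + 33 = Day 370. Exposure: 370 − 1 + 1 = 370 days.
- Study completion: Day 365. Exposure if capped: 365 days.
- Overrun: 370 − 365 = 5 days (Days 366 to 370), and 5/370 = 1.35%.
- On-treatment period 370 days; on-study period 365 days.
- Post-treatment period: starts on Day 371, ends on Day 365.

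**Within the visit windows.** Overrun = max(0, 33 − gap), where gap is the number of days from last dose to enrolment.

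| Gap (days) | Overrun (days) |
|---|---|
| 33 or more | 0 |
| 28 | 5 |
| 23 | 10 |
| 18 | 15 |

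The largest case is a Week 48 dose on Day 342 and enrolment on Day 360: 15/360 = 4.2% of the capped exposure. If the two visit deviations were independent and uniform on −5 to +5 (an assumption for scale only), the mean overrun would be 5 + 35/121 = 5.3 days.

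**Effect on an arm's rate.** With every subject dosed to Day 337, mean exposure is 370 days as written and 370 − 5r if capped, so the rate is understated by 5r/370. Uncapped subject-years per arm: 530 × 370/365.25 = 536.9.

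| r | Capped subject-years | Understatement |
|---|---|---|
| 25% | 535.1 | 0.34% |
| 50% | 533.3 | 0.68% |
| 75% | 531.5 | 1.01% |
| 90% | 530.4 | 1.22% |
| 100% | 529.6 | 1.35% |

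Illustration: if 60% of subjects had an AE (assumed) and all rolled over, the reported rate would be 318/536.9 = 59.2 per 100 subject-years instead of 318/529.6 = 60.0.

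**Effect on the ratio between arms.** If roll-over were 90% in one arm and 70% in the other: (370 − 4.5)/(370 − 3.5) = 0.9973, a shift of about 0.3%. The extreme of 100% against 0% gives 365/370 = 0.9865.

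**The case against.** The case for leaving the rule alone has five parts.

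- **Efficacy may already be capped.** SAP 3.1.4 describes the planned treatment period as covering both on- and off-treatment time and ends it at the Week 52 visit. SAP 3.1.5 flags records as on- or off-treatment from within that period. On that reading, on-treatment exacerbation time stops at Week 52. This shows some ambiguity, but SAP 3.2.1.1 sends the reader directly to 2.1.5 for the on-treatment time at risk, and the argument does not reach safety exposure in 3.3.1.
- **Enrolment at Day 365 is assumed.** This is so. Anyone enrolling 33 or more days after the last dose, including subjects deferred under the COVID-19 rule, has no overrun. The concern is limited to those entering at Week 52.
- **The 1.35% is a ceiling.** It needs every subject to be dosed at Week 48 and to roll over at once, while the sample-size section assumes 10% dropout. The realistic figure is lower and cannot be derived from the documents.
- **The rate is openly crude.** SAP 3.3.1 ignores gaps from missed doses, each of them 28 days, and SAP 3.3.2 keeps full exposure after a first event. Those are declared simplifications about time within the study. They do not justify counting time outside it.
- **No conclusion changes.** This stands. The primary time at risk is bounded by Visit 17 or the last exacerbation assessment (SAP 3.2.1.1), and study-adjusted AE rates use the on-study period, which does end at enrolment.

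**Conclusion.** The concern holds, at low severity. As written, a completer who enters the extension less than 33 days after the last dose is credited with exposure beyond the end of the study: 5 days on nominal timing and 0 to 15 days within the visit windows. Absolute exposure-adjusted rates are understated by at most about 1.4% on nominal timing, in proportion to the unknown share rolling over at Week 52. Both arms are affected similarly, so treatment comparisons barely move. There is no effect on completers who stay for Week 58 and 64 follow-up, on subjects whose Week 48 dose was skipped, or on the primary analysis. The inconsistency between the on-treatment, on-study and post-treatment periods exists whatever the share.

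**What to change.** Add the date of study completion (the day of enrolment in the extension, where applicable) as a further term in each minimum. There are six occurrences in four sections: two in SAP 2.1.5, two in 3.1.6, and one each in 3.3.1 and 3.3.2.

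In 3.1.6 and 3.3.2 the change is for consistency. Records after enrolment are already excluded, so no record should be reclassified. The numerical change comes in extent of exposure and in the on-treatment exacerbation time at risk. On nominal timing an entrant's exposure becomes 365 days instead of 370, and the post-treatment period becomes empty (it would start on Day 366 and end on Day 365) instead of negative. A Week 52 visit held on or before enrolment remains on-treatment, so the purpose of the 33-day allowance is kept. Completers who stay for follow-up are unchanged, because their completion date falls after last dose plus 33 days.

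The cost is one added term per formula, using a date the SAP already defines.
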